2.1 Primary Objective

This is a non-randomized, single arm pilot study of 10 participants to investigate the effect of interferon alpha on HIV-1 production in plasma and peripheral blood lymphocytes from HIV-infected individuals with HIV-1 RNA levels below the limit of detection in commercial assays.

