Secondary analyses will attempt to identify individual intensification responders. One definition of responder is whether the patient had at least a 1-log decrease from baseline to 4 weeks in viral load. Because patients with baseline viral load below 10 cannot achieve this, another method will compute the least squares slope of viral load versus time for each patient and declare patients with statistically significant slopes as responders. Because the goal for this analysis is to summarize the response of a given individual, we treat the data as independent observations from that patient. This is the same assumption made when using a mixed model, namely that conditioned on the random, patient-specific intercept and slope, the observations are independent. For both the 1 log method and significant slope method of identifying individual responders, we attempt to find differences in baseline characteristics between responders and non-responders, though very low power precludes finding any of these statistically significant unless they are huge. Of particular interest is whether baseline viral load predicts responder status. As described above, for this analysis we will use one baseline value to characterize baseline viral load and another for the calculation of slope to identify responder status.

All tests will be two-sided and an alpha level of less than 0.05 will be considered statistically significant. Analyses will be performed on both intent-to-treat and as per protocol participants. Any dropouts and non-adherent participants will be replaced. We do not feel that stopping criteria are necessary as this pilot study is not for prognosis or clinical management; there is no blinding of study treatment and we will be monitoring toxicities in real time. In this study, we will be studying participants on an ongoing basis, and no interim analysis is planned.

11 Sample Size Estimation

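### Whether baseline viral load predicts response is examined only on a responder split of 10 people; a continuous analysis with a censoring rule should be added

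*Combined protocol and SAP*

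**What the plan says.** The study is small by design: "This is a non-randomized, single arm pilot study of 10 participants". Section 10 asks whether viremia falls consistently across patients (the primary question) and whether it falls in any individual patient.

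For the first question, Section 10 compares pre-intensification with week-4 values by a paired t-test. It also computes a slope per participant and tests whether the mean slope is zero. These are continuous measures, used only for the population mean.

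For the second question, each participant is classed as a responder or not, in two ways. One is "at least a 1-log decrease from baseline to 4 weeks in viral load". The other is to "declare patients with statistically significant slopes as responders". The search for predictors rests on that classification, and the plan concedes the difficulty: "we attempt to find differences in baseline characteristics between responders and non-responders, though very low power precludes finding any of these statistically significant", with huge differences excepted. The stated interest is: "Of particular interest is whether baseline viral load predicts responder status". The plan sets a sensible safeguard: "for this analysis we will use one baseline value to characterize baseline viral load and another for the calculation of slope". The significance rule is general: "All tests will be two-sided and an alpha level of less than 0.05 will be considered statistically significant".

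The test for this comparison is not named, and no power figure is given. Nowhere is the continuous change or slope related to baseline viral load. The Introduction mentions correlations with response, but for interferon-inducible gene expression.

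**The concern.** Section 10 presents very low power as a property of the sample size. Part of it comes from turning a measured change into yes or no before asking what predicts it. With 10 people the split may be 1 against 9 or 2 against 8, or there may be no split.

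Few responders is a case the plan itself contemplates. Section 11 says responses may resemble earlier antiretroviral intensification, in which nobody's viral RNA fell. In that case the question that Section 10 picks out could not be examined by the planned method, although changes and slopes would still be available.

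**Working it through.** **Inputs from the documents.** n = 10 (Section 2.1); two-sided 0.05 and two binary responder definitions (Section 10); assay lower limit 0.1 copies/mL (Section 13). The responder rate is stated to be undefined (Section 11).

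**Assumptions.** Correlation between baseline and change 0.3 to 0.9; responder share 10% to 50%; bivariate normal, uncensored data unless stated.

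**The plan's own figure.** There is none for this comparison. The only numerical basis for n = 10 is the exact bound after 0 of 10. The two-sided 90% bound is 1 − 0.05^(1/10) = 0.259, the table's 0.26. The one-sided 90% bound is 1 − 0.10^(1/10) = 0.206, the text's 21%. Neither bears on power for predictors.

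**Step 1: can the split be tested?** With responder probability p, the chance of no split is (1−p)^10 + p^10, and the chance of exactly one responder is 10p(1−p)^9.
- p = 0.10: no split 0.35; one responder 0.39.
- p = 0.20: no split 0.11; one responder 0.27.

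With k responders of 10, the smallest two-sided exact rank-sum p is 2/C(10,k):
- k = 1: 2/10 = 0.20
- k = 2: 2/45 = 0.044
- k = 3: 2/120 = 0.017

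**Step 2: power.** Simulation with 12,000 trials per cell: Pearson test of baseline against change, compared with a two-sample t-test of baseline by responder status. Repeat runs differed by about one percentage point. Percentage lost is 1 − (t-test power / Pearson power).

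| Correlation | Responders | Pearson | Responder t-test | Power lost |
|---|---|---|---|---|
| 0.5 | 50% | 0.315 | 0.202 | 36% |
| 0.5 | 20% | 0.329 | 0.153 | 53% |
| 0.5 | 10% | 0.327 | 0.108 | 67% |
| 0.7 | 50% | 0.676 | 0.422 | 38% |
| 0.7 | 30% | 0.679 | 0.364 | 46% |
| 0.7 | 20% | 0.682 | 0.296 | 57% |
| 0.7 | 10% | 0.689 | 0.187 | 73% |
| 0.8 | 50% | 0.865 | 0.582 | 33% |
| 0.8 | 10% | 0.868 | 0.245 | 72% |

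Spearman has about 58% power at correlation 0.7 and 77% to 78% at 0.8. An exact Mann-Whitney test on the split does worse than the t-test: at 0.7 it has 34%, 28%, 21% and 10% power for 50%, 30%, 20% and 10% responders. Pearson power at weaker correlations is 13% at 0.3, 21% at 0.4, 32% at 0.5 and 48% at 0.6.

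**Step 3: the significant-slope rule itself.** This was simulated with five weekly points from Day 0 to Day 28, an assumed mean fall of 0.3 or 0.77 log, slope SD 0.4 or 0.8, residual SD 0.2 or 0.4, and correlation 0.6 to 0.95. The 0.77 is borrowed from the 12-week result in untreated patients cited in the Introduction. The split kept 18% to 69% of the continuous power and lost more than half in 19 of 24 scenarios.

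**Step 4: values below the assay limit.** Here everyone has the same expected fall, so baseline truly predicts nothing. Predictor and change use separate baselines, and values below 0.1 copies/mL are set to 0.1. Assumed SDs are 0.5 log between people, 0.25 for the assay and 0.2 for the fall. With a 0.77 log fall, the continuous test rejected in about 8%, 18% and 48% of trials at mean baselines of 2, 1 and 0.3 copies/mL. With a 0.3 log fall it rejected in about 5% to 12%. In a repeat the ranges were 9% to 49% and 5% to 11%, against 1% to 12% for the 1-log split. The nominal rate is 5%.

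**The case against.** The strongest defence is that this is a secondary, openly exploratory analysis in a pilot, whose low power is disclosed. That limits the weight of the point. It does not explain why information already computed goes unused on a question the plan calls of particular interest.

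Three further objections stand in part:

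- **The continuous analysis is no cure.** Below a correlation of about 0.6 it also misses more often than it finds, which is not far from the plan's own caveat about huge differences.
- **Change is not fully measured in everyone.** The Précis and Introduction expect some patients below the assay's detection limit, and inclusion criterion 4 requires cell-associated rather than plasma RNA. The uncensored power figures are therefore optimistic. Step 4 shows that a continuous analysis with limit substitution can be worse than the split for false positives.
- **Responder status is a deliberate target.** It serves the plan's question whether any individual responds, which a regression on baseline does not answer. The responder comparison should stay.

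Two stronger readings are tempting but unsupported. A reader might infer that dichotomising always costs more than half the power. With a t-test and 30% to 50% responders it costs about a third to just under a half, and the documents fix neither the test nor the rate. A reader might also infer that the trial will wrongly report that no predictor exists. Section 10 commits to no such statement. The 0.20 floor with one responder applies to a rank test, which the plan does not name.

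**Conclusion.** The point holds in a bounded form. The predictor question is examined only on a binary response in 10 people, and no continuous counterpart is planned. For correlations of 0.5 to 0.8 with a t-test, the split loses about one third to nearly three quarters of the power, and more than half when about 20% or fewer respond. With no responders there is no test.

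The practical gain is mainly for strong associations, around 0.7 or more. All power figures rest on assumed correlations, responder shares and normal, uncensored data. The primary analysis is unaffected. A continuous analysis is worth adding only with a proper method for values below the limit.

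**What to change.** Add to Section 10, alongside the responder comparison:

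1. In all participants, relate the log10 change from Day 0 to Day 28, and the slope, to the separate Pre-Entry 1 single-copy value, with a confidence interval. Do the same for the other baseline characteristics.
2. Treat values below 0.1 copies/mL as left-censored, for example by a censored-normal regression of the week-4 value, with the model and hypothesis written out. Do not substitute the limit. Add a sensitivity analysis limited to participants whose baseline is well above it.
3. Keep the rule of one baseline for the predictor and another for the change, and name the visits.
4. Keep the responder analysis for the question whether any individual responds, and name its test.

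The single-copy assay is already scheduled at Pre-Entry 1, Day 0 and Day 28, so no new visits, samples or participants are needed. The cost is SAP wording and slightly more analysis work. The result stays exploratory.

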With respect to HIV, INF has shown antiviral activity both in vitro (Ho, Hartshorn et al. 1985) and in vivo (Lane, Kovacs et al. 1988, Hatzakis, Gargalianos et al. 2001). The major activity of INF against HIV is thought to be the inhibition of the release of progeny virions from host-infected cells (Poli, Orenstein et al. 1989, Gottlinger, Dorfman et al. 1991). This anti- HIV-1 activity is opposed by the viral protein Vpu (Gottlinger, Dorfman et al. 1993) and recently the cell protein that mediates viral retention was identified as an INF-induced protein, Bst-317 or tetherin (Neil, Zang et al. 2008). In addition it is known that retroviral restriction factors such as APOBEC3G and TRIM5 α are INF-regulated genes and their induction might also play a role in INF antiviral activity (Goff 2004). A number of in vitro studies suggested that the effects of interferon were modest (2-8 fold reductions in viral RNA) but interestingly, the combination of interferon and early antiretrovirals, such as AZT, was markedly synergistic (Hartshorn, Vogt et al. 1987), including in vitro models of cells chronically infected with HIV-1. These results are particularly intriguing because in cultures of chronically infected cells, the majority of the cells produce HIV-1 from integrated proviruses, and there is little spreading infection; as a result, AZT has minimal or no direct antiviral effect, and interferon may have been the most potent antiviral in these experiments (Poli, Orenstein et al. 1989). Experiments with HIV-1 production from chronically infected cells may represent a

useful model for participants suppressed on antiretroviral therapy as experiments suggest the majority of the detectable virus is produced from cells with integrated proviruses. Although interferon has been studied in active spreading infections, little data are available from participants who are already suppressed on ARV.

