In the pre-ART era, INF clinical trials showed a degree of efficacy in reducing viral replication, p24 production, and slowing progression to AIDS (de Wit, Schattenkerk et al. 1988, Lane, Davey et al. 1990, Berglund, Engman et al. 1991). After development of combination ARV, however, INF was not developed as an antiretroviral, due to lower antiviral efficacy, inconvenient route of administration, and adverse effects (Lane, Davey et al. 1990, Dusheiko 1997). Recently, several groups have shown a substantial HIV RNA reduction in participants treated with the pegylated form of interferon alpha (PEG-INF) as part of chronic hepatitis C therapy (Torriani, Ribeiro et al. 2003, Talal, Shata et al. 2004, Neumann, Polis et al. 2007). In addition, Asmuth and colleagues recently studied the effect of pegylated interferon alpha on HIV viral load in HBV/HCV seronegative HIV-1-infected participants who were not receiving antiretroviral therapy. HIV-1 viremia declined by a mean 0.77 log₁₀ copies/mL over 12 weeks (Asmuth D 2009).

The mechanism of interferon effect on HIV viremia is uncertain. There is a substantial literature regarding the effects of interferon in retroviruses in vitro, and in HIV in particular (Pitha 2011). Interferon may induce expression of a number of innate immune responses, which have direct effects on a number of distinct steps in virus replication. Induction of the cellular gene APOBEC 3G and 3F can result in hypermutation of the HIV genome during reverse transcription (Goila-Gaur and Strebel 2008). Induction of the gene tetherin results in retention of HIV on the surface of infected cells and decreases in production of extracellular HIV virions (Perez-Caballero, Zang et al. 2009). The effects of interferon may be manifest as a decrease in peripheral viremia, and a corresponding accumulation of HIV RNA intracellularly.

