This is a pilot study of the effect of pegylated interferon on HIV-1 RNA levels in participants who are receiving antiretroviral therapy. To date, there is limited published data available, and the proportion of participants who will respond with decreases in HIV-1 viral RNA levels remains to be clearly defined. As described above, responses may be similar to those observed with PI, integrase inhibitor, or NNRTI intensification, where no participants have experienced a decrease in viral RNA levels. If so, previous sample size analyses estimating the frequency of suppressible participants are relevant. In the accompanying table, we estimate the 90% confidence intervals of the probability that a participant has a detectable decrease in viral RNA levels (participants suppressed in the table below) after studying increasing numbers of participants without observing episodes of drug suppression. As shown here, if we study 10 participants and observe no

suppression in plasma or cell-associated HIV RNA, we have 90% confidence that the frequency of suppressible participants is less than 21%. For this pilot study, we will request a sample size of 65 participants to achieve our goal of studying 10 participants who have ≥ 0.1 copies/mL HIV-1 RNA at screening.

90% exact confidence intervals (using the Clopper-Pearson method) for the probability of being suppressible.

Participants intensified	Participants suppressed	90% confidence interval
5	0	0,0.45
6	0	0,0.39
7	0	0.0.35
8	0	0,0.31
9	0	0,0.28
10	0	0,0.26
15	0	0,0.18
20	0	0,0.14

12 Hazards/Discomforts/Risks

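### Section 11 states the 0-of-10 limit as a bound on suppressible participants, but it bounds only participants in whom a decrease is detected

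*Combined protocol and SAP*

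**What the plan says.** Section 11 defines its binomial event as "the probability that a participant has a detectable decrease in viral RNA levels (participants suppressed in the table below"), that is, a decrease that is detected. The table is headed "90% exact confidence intervals (using the Clopper-Pearson method) for the probability of being suppressible", and its row for 0 of 10 gives an upper limit of 0.26. The text applies this to 10 participants with no observed "suppression in plasma or cell-associated HIV RNA" and concludes that "we have 90% confidence that the frequency of suppressible participants is less than 21" per cent. It does not say what observation counts as suppression or how the two compartments are combined.

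Section 10 (Statistical Considerations) has the only rules for classifying an individual. "One definition of responder is whether the patient had at least a 1-log decrease from baseline to 4 weeks in viral load". It adds that this cannot be achieved from a baseline below 10, and so offers a second rule: a statistically significant least-squares slope for that patient. No sensitivity, within-person SD, measurement scale or time window for the slope is given.

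Section 1 quantifies interferon's effect twice. In vitro, "the effects of interferon were modest (2-8 fold reductions in viral RNA"). In people not on ART, "HIV-1 viremia declined by a mean 0.77" log10 copies/mL over 12 weeks.

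**The concern.** The probability that a participant is observed to decrease is not the proportion of participants who can be suppressed. The two agree only when every suppressible participant is detected (sensitivity 1) and no one else is. Section 11 moves from one to the other without stating that condition.

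The step matters most if the result is null, which Section 11 treats as plausible because earlier intensification studies saw no decreases. Its sentence would then be the ready-made numerical conclusion, and the trial would claim to exclude a frequency of suppressible participants that it may not have excluded.

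**Working it through.** **1. The plan's own figure.** For 0 of n, the upper limit is 1 − α^(1/n).
- One-sided 90%: 1 − 0.10^(1/10) = 0.2057, the text's figure of less than 21%.
- Two-sided 90% Clopper-Pearson: 1 − 0.05^(1/10) = 0.2589, the table's 0.26. All eight table rows reproduce on this basis.

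Both are correct for detected decreases. They use different conventions, which should be reconciled. The steps below use the text's 0.2057.

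**2. Limit for truly suppressible participants.** Let θ be their frequency, s the sensitivity of the rule and φ its false-positive rate. The data bound sθ + φ(1 − θ) by 0.2057, so θ ≤ (0.2057 − φ)/(s − φ), capped at 1.
- With φ = 0: 0.2057/0.8 = 26%; 0.2057/0.5 = 41%; 0.2057/0.3 = 69%; at s of about 0.2 or less there is no information.
- With φ = 0.025 (a downward slope at two-sided 0.05), 21% is kept only if s ≥ 0.025 + (0.2057 − 0.025)/0.21 = 0.885.

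**3. What the documents alone say about s.** A 2-8 fold reduction is log10(2) to log10(8), or 0.30 to 0.90 log. These falls and 0.77 are below 1 log. For a true fall below 1 log with symmetric error, the 1-log rule detects fewer than half, whatever the SD. Section 10 itself says that the rule fails below a baseline of 10.

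**4. Illustration.** Assumptions not in the documents: log10 scale; independent normal error with SD 0.1 to 0.4; a true fall of 0.77 log by week 4; one RNA series; a participant counts if either rule is met, with the slope downward.
- 1-log rule: s = Φ((0.77 − 1)/(SD√2)) = 5%, 21%, 29%, 34% at SD 0.1, 0.2, 0.3, 0.4.
- Slope rule, linear fall, samples on Days 0, 7, 14, 21 and 28 (Sections 5.4 to 5.6): Sxx = 4 + 1 + 0 + 1 + 4 = 10, 3 residual df, critical t 3.18, noncentrality (0.77/4)√10/SD = 0.609/SD. Sensitivity is 97%, 54%, 30%, 19%.

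Sensitivity of either rule, from simulation, with the resulting limit in brackets:

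| Samples and shape of fall | SD 0.1 | SD 0.2 | SD 0.3 | SD 0.4 |
|---|---|---|---|---|
| Days 0-28, linear | 0.97 (0.19) | 0.59 (0.32) | 0.43 (0.44) | 0.40 (0.44) |
| Days 0-28, rapid then flat | 0.06 (1.0) | 0.25 (0.79) | 0.33 (0.58) | 0.37 (0.48) |
| Plus one pre-entry sample, linear | 0.95 (0.20) | 0.68 (0.28) | 0.52 (0.35) | 0.47 (0.36) |
| Plus one pre-entry sample, rapid then flat | 0.58 (0.33) | 0.50 (0.38) | 0.47 (0.40) | 0.45 (0.37) |

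The pre-entry sample is scheduled (Section 5.2, Appendix 1); Day −14 is assumed. The false-positive rate is about 0.025 at SD 0.1 and 0.2, 0.03 at 0.3 and 0.055 to 0.06 at 0.4. Worked cell (first row, SD 0.2, s = 0.587 before rounding): (0.2057 − 0.025)/(0.587 − 0.025) = 0.1807/0.562 = 0.32.

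**The case against.** The strongest reply is that Section 11 defines its event as a detectable decrease, and for that event 20.6% is right. This stands: the fault is in interpretation, and a reader who infers an arithmetic error would be wrong.

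A reader might also infer that the sample size loses its only support. It does not. Section 1 also cites useful results from earlier intensification studies of this size, and Section 13 reports that 9 of 10 enrolled in the raltegravir study completed with evaluable data. Section 10 puts primary emphasis on the population analysis (paired t-test, Wilcoxon test, mean slope with confidence interval). Individual responders are secondary.

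Third, the sizes above rest on choices that the documents do not settle. At SD 0.1 with a linear fall the bound is kept. The limit of 1.0 needs low noise, a rapid fall and no pre-entry sample in the slope; one such sample brings it to 0.33. The 0.77 figure is a 12-week mean off ART, so placing it at week 4 on ART is an assumption, and a mean below 1 log does not show that every individual's fall is. The 2-8 fold figure is in vitro. So the documents do not support a claim that the limit must be any particular larger value.

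Finally, Section 11 does not say that Section 10's rules define suppression, and it also counts cell-associated RNA, which could raise combined sensitivity. The direction is uncertain: Section 1 expects that RNA may accumulate inside cells. An unnamed rule has no known sensitivity, so this does not rescue the sentence. Section 10's disclosure about baselines below 10 is to its credit, but Section 11 does not carry it forward.

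**Conclusion.** The point holds as an overstatement of what 0 of 10 shows. The limit of 20.6% (25.9% two-sided) applies to participants who would show a detected decrease. Extending it to suppressible participants requires sensitivity of essentially 1, which the plan neither states nor supports.

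That the wording overreaches follows from the documents alone. By how much does not: it depends on the within-person SD, the size and shape of the fall, the samples used and the treatment of cell-associated RNA. In the cases tabulated, the limit stays near the stated figure only at SD 0.1 with a linear fall; elsewhere it is 0.28 or more. Severity is moderate: the sentence governs a secondary, individual-level conclusion and leaves the primary analysis untouched.

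**What to change.** In Section 11:
- Restate the sentence so that 0 of 10 bounds the frequency of participants who meet a named detection rule. Give its scale, time window and direction, and say how plasma and cell-associated RNA are combined.
- Say that the limit for truly suppressible participants is larger when sensitivity is below 1, and show it over assumed sensitivities, for example 20.6%/s: 26% at 0.8 and 41% at 0.5. No trial data are needed for this.
- Use one confidence convention in text and table.
- Rest any conclusion of no effect on the confidence interval for the mean change from the primary population analysis.

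The cost is a few sentences and a less favourable stated figure. No extra participants or visits are needed.

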3.2.3 Sample Size

As described below (see Statistical Considerations) we expect that 10 participants completing the study will be necessary to yield useful clinical information. In order to enroll 10 participants for this study, we will be screening up to 65 individuals. Any dropouts and non-adherent participants will be replaced.

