4.1 Inclusion Criteria

To be eligible for study participation, a volunteer must satisfy all of the following inclusion criteria:

1. Age ≥ 18 years.
2. Documentation of HIV-1 infection by any licensed ELISA test and confirmed by a Western Blot.
3. Receiving a DHHS-approved ARV regimen,.
4. Level of cell-associated HIV RNA ≥ 5 copies/million peripheral blood mononuclear cells (PBMC) done at screening visit 1
5. HIV-1 RNA levels less than detectable by current commercial means (e.g., Roche Amplicor, b-DNA test) for a minimum of 12 months prior to screening at all time points, and with at least 2 measurements in this 12 month window.

6. CD4 ≥ 300 cells/mm³ at pre-entry visit within 14 days prior to enrollment.
7. Ability to sign informed consent and willingness to comply with the study requirements and clinic policies.
8. No evidence of viral hepatitis co-infection as assessed by Hepatitis C antibody, HCV RNA, and hepatitis B surface antigen; determinations at pre-entry visit within 28 days prior to enrollment.
9. No history of or evidence of autoimmune hepatitis or other autoimmune disorders at screening, or antinuclear antibody (ANA $> 3x$ upper limit of normal).
10. Laboratory values at pre-entry visit within 14 days prior to enrollment:
 - Alkaline phosphatase < 2.0 times upper limit of normal
 - Alanine transaminase (ALT) < 2.0 times upper limit of normal
 - Total bilirubin < 2.5 mg/dL (< 40 mg/dL if on Atazanavir)
 - Creatinine clearance ≥ 60 mL/min as estimated by the Cockcroft-Gault equation
 - Neutrophil count ≥ 1500 cells/mm³
 - Platelets $\geq 150,000$ / mm³
 - Hemoglobin ≥ 12.0 mg/dL for men and > 11.0 g/dL for women
 - Fasting glucose < 126 mg/dL
11. No history or evidence of significant clinical depression at screening that in the opinion of the investigator would affect the ability of the patient to participate in the study, or which would constitute a threat for his/her health in case of relapse upon INF treatment. The Beck Depression Inventory score must be ≤ 13 at pre-entry visit.
12. No history of INF/PEG-INF therapy.
13. If capable of pregnancy: use of effective contraception during study: effective contraception methods include abstinence, surgical sterilization of either partner, barrier methods such as diaphragm, condom, cap or sponge, or use of hormonal contraception with an anti-HIV regimen that will not alter metabolism of hormonal contraception.

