5.1 Screening (Days -58 to -28)

Screening will consist of HIV-1 RNA level and if < 50 copies/mL by standard assay and have detectable PBMC-associated HIV RNA ≥ 5 copies/million cells will continue with screening. If > 50 copies/mL, the subject will not undergo further screening assessments.

Screening for the protocol will be completed within 4 weeks prior to the study enrollment. During screening visit the protocol design will be reviewed, and informed consent will be obtained prior to any study-related screening procedures. The subject will then be given the consent document to read. Consent forms may be sent to the subject for review prior to the screening visit. The site investigator will review the study with the subject and answer any questions the subject may have about the study design, interferon, or study procedures. After the subject has read this information, there will be further opportunity for discussion with one of the investigators. Potential participants will sign consent prior to any study-related procedures. Once consented, eligibility will be assessed.

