12.2 Human Subject Protections

Participants will be fully counseled prior to entry into the study as to the potential risks of the study. Participants who, in the opinion of the study team, do not fully comprehend these potential risks will not routinely be offered participation in the study. Participants will be monitored closely during their participation in the study, and informed of any new information regarding the study treatment that may influence their willingness to continue study participation.

13 Study Recruitment

The study will be advertised and posted on the NIH web site. The University of Pittsburgh AIDS Clinical Trials Unit will recruit participants from its Volunteer Registry. IRB-approved recruitment materials will be distributed among AIDS service organizations and other HIV providers in the region. Both the NIH and the University of Pittsburgh have recently completed drug intensification studies and have been successful in enrolling participants willing to complete the frequent visits.

In the most recent study, we used the current viral RNA enrollment criterion (≥ 0.38 copies/mL) to study raltegravir intensification; 36 participants were screened for the study and 10 were eligible; the remainder were excluded chiefly on the basis of viral RNA levels. Nevertheless, 9 of the 10 enrolled participants completed this study and had evaluable data that were useful in determining whether viremia decreased. To improve our statistical analysis, we have increased the sensitivity of the assay (lower limit of quantification = 0.1 copies/ml) and will use 0.1 copies/ml as cutoff.

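### Sections 11 and 13 assume a plasma floor of 0.1 copies/mL that Sections 4.1 and 5.1 do not contain, and Section 10 has no rule for plasma values below the assay limit

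*Combined protocol and SAP*

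**What the plan says.** **Planning sections.** Section 11 states "we will request a sample size of 65 participants" in order to "achieve our goal of studying 10 participants who have ≥ 0.1 copies/mL HIV-1 RNA at screening". The unit and the assay context make this a plasma quantity. Section 13 describes an earlier raltegravir study that enrolled at 0.38 copies/mL or more, in which "36 participants were screened for the study and 10 were eligible". It then gives 0.1 copies/mL as the improved assay's lower limit of quantification and says the study "will use 0.1 copies/ml as cutoff". Section 3.2.3 says "In order to enroll 10 participants for this study, we will be screening up to 65 individuals".

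**Eligibility sections.** Inclusion criterion 4 in Section 4.1 is "Level of cell-associated HIV RNA ≥ 5 copies/million peripheral blood mononuclear cells (PBMC) done at screening visit 1". Criterion 5 sets only a plasma ceiling, the commercial assay limit. Section 5.1 lets people proceed if they are under 50 copies/mL and "have detectable PBMC-associated HIV RNA ≥ 5 copies/million cells will continue with screening". The single copy assay (SCA) is run at screening (Section 9.2, Appendix 1), but no threshold is attached to it. The Précis and Section 1 say that some participants may be below the plasma limit and that they are to be studied.

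**Analysis section.** The primary analysis in Section 10 is a paired t-test of viral load, pre-intensification against week 4, two-sided at 0.05. No rule is given for values below the limit. Section 10 also says that a baseline under 10 rules out a 1-log fall.

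**The concern.** Two parts of the plan describe different study populations. The planning sections count on 10 people whose plasma RNA can be quantified. The eligibility sections admit people whose plasma RNA cannot.

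A participant whose analysis baseline is below the limit can show little or no measurable plasma fall, yet still counts as one of the 10 in a plasma paired test. Three things follow:

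- A statement about plasma alone may rest on fewer than 10 people.
- With no below-limit rule and two different implied limits, the plasma estimate and the responder count depend on choices that could be made after the data are seen.
- The stated reason for 65 refers to a criterion that is not in force.

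**Working it through.** **1. The plan's own bound.** For 0 responders of n, the exact upper limit is 1 − a^(1/n).

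- With a = 0.10 (one-sided 90%) and n = 10: 1 − 0.10^(0.1) = 0.206, the 21% in the text of Section 11.
- With a = 0.05 (two-sided 90%) and n = 10: 1 − 0.05^(0.1) = 0.259, the 0.26 in its table.

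Both reproduce, on different conventions. The table's convention is used below.

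**2. A plasma-only bound.** Let k be the number of the 10 with a measurable plasma baseline. The documents do not give k, so a range is shown.

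| k | 1 − 0.05^(1/k) |
|---|---|
| 10 | 0.26 |
| 9 | 0.28 |
| 7 | 0.35 |
| 5 | 0.45 |

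**3. Ceiling on the paired t-test.** Assume n = 10 and that the other 10 − k plasma changes are exactly zero (both values below the limit and set to the same number). For a given k, |t| is largest when the k falls are equal. With each fall equal to d, the mean is kd/10 and the variance is [kd²(10 − k)/10]/9, so |t| = 3·√(k/(10 − k)). The two-sided 0.05 critical value on 9 df is 2.262.

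- k = 3: 3·√(3/7) = 1.96, p = 0.081. Significance is out of reach.
- k = 4: 3·√(4/6) = 2.45, p = 0.037. Significance is possible.

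At k = 4 the falls need not be equal. If c is their SD (divisor 4) over their mean, |t| = 3.795/√(2.4 + 4c²), which stays above 2.262 up to c of about 0.32. For example, falls of 0.55, 0.9, 1.1 and 1.4 with six zeros give t = 2.27, p = 0.049. Rises among the other participants would only lower |t| for a fall.

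**4. The assay limit.** The lowest baseline from which a 1-log fall can be seen is 10 × the limit. Section 10's figure of 10, read in copies/mL, implies a limit of 10/10 = 1 copy/mL. At Section 13's limit of 0.1 the threshold is 10 × 0.1 = 1 copy/mL. Baselines from 1 to just under 10 are therefore said to be incapable of a fall that the Section 13 assay could show.

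**5. Why a below-limit rule matters.** Take a baseline of 0.38 copies/mL (the earlier study's criterion) and a week 4 value below 0.1. The recorded fall is:

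- log10(0.38/0.1) = 0.58 if the week 4 value is set to the limit;
- log10(0.38/0.05) = 0.88 if it is set to half the limit;
- log10(0.38/0.01) = 1.58 if it is set to one tenth of the limit.

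The last choice makes the participant a 1-log responder; the other two do not.

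**6. The 65.** Ten of 65 is a yield of 15.4%. The only yield given is 10/36 = 27.8% (exact 95% interval 14% to 45%), at 0.38 copies/mL in plasma. At that yield, 65 × 10/36 = 18.1 eligible are expected, and the binomial probability of at least 10 is 0.99. It is 0.86 at a 20% yield and 0.52 at 15%. No yield is given for the cell-associated criterion.

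**The case against.** The strongest reply has four parts.

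- **The bound is not claimed for plasma alone.** Section 11 speaks of no suppression in plasma or in cells, and criterion 4 makes every participant measurable in cells at screening. This stands. A reader might infer that the mismatch invalidates the 21%/26% bound. It does not; only a plasma-only statement is affected.
- **Section 10 is not silent on compartment.** It asks about viremia, and Sections 2.2 and 3.1 tie viremia and viral load to the single copy assay. This also stands: the t-test reads as plasma SCA. What remains open is the role of cell-associated RNA. Section 3.2.2.1 puts lymphocyte RNA under the primary end points, while Section 3.2.2.2 lists HIV RNA and DNA by droplet PCR as secondary. The documents do not support insisting that both be primary.
- **Below 0.1 on one draw is not zero change.** SCA is taken at screening, pre-entry 1 and entry, and Section 10 uses separate baselines for eligibility and for change. This is fair. It is why k must be defined on the analysis baseline, and why the t-test results are limits and not forecasts.
- **65 is a ceiling.** A reader might infer that 65 is too few. The documents show no shortfall: at the only yield they give, 65 is ample. What fails is the stated reason.

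That this is a pilot does not remove the point. The plan still names a primary test at 0.05 and a numerical bound.

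**Conclusion.** The plan is inconsistent as written and should be corrected. The 0.1 copies/mL floor in Sections 11 and 13 has no counterpart in Sections 4.1 and 5.1, so the eligibility rules do not secure 10 plasma-measurable participants. Section 10 lacks a below-limit rule and implies a limit ten times the one in Section 13. These conclusions come directly from the text; the tenfold gap assumes that the 10 in Section 10 is in copies/mL.

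The size of the consequence depends on k, which is unknown. A plasma-only upper limit moves from 0.26 at k = 10 to 0.45 at k = 5. The t-test ceiling at k of 3 or fewer rests on the further assumption that all other plasma changes are zero. Nothing in the documents says that k will be this low, so it would be wrong to conclude that the primary test is bound to fail.

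**What to change.** **If Section 4.1 stands:**

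- In Sections 11 and 13, replace the 0.1 copies/mL goal and cutoff with the cell-associated criterion.
- In Sections 3.2.3 and 11, restate the basis for 65, with an assumed yield for that criterion.
- Base any plasma-only bound on the number whose non-screening baseline SCA is at or above 0.1 copies/mL. The table in Section 11 already has rows for 5 to 9.

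**In Section 10:**

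- State one SCA limit and correct the sentence about baselines under 10 to match it.
- Prespecify a left-censored analysis of the baseline to week 4 plasma change alongside the paired t-test.
- Reconcile Sections 3.2.2.1, 3.2.2.2 and 10 on whether cell-associated RNA is primary or secondary. Name the samples that supply its baseline and week 4 values, since Sections 5.4 and 5.6 list PBMC only for storage. If both compartments are primary, acknowledge two tests at 0.05, with a chance of at least one false positive of up to 2 × 0.05 = 0.10.

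**Cost:** wording, one added analysis and no change to eligibility. The plasma-only precision may look less favourable, and 65 may change once a yield is stated.

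**If a plasma floor is intended instead:** state it in Sections 4.1 and 5.1 and base 65 on meeting both criteria. This would make recruitment harder and could affect participants already enrolled, as one site completed enrolment in 2014. It would not by itself guarantee a measurable value at the separate analysis baseline.
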